9. INVESTIGATIONAL PLAN

9.1. VISIT SCHEDULE

Details of study procedures are in the Study Calendar.

9.1.1. Screening Period

Therapeutic Parameters

Pre-study scans used to assess all measurable or non-measurable sites of disease must be done within **4 weeks** prior to registration.

Pre-study complete blood count (with differential and platelet count) should be done ≤ 4 weeks before registration.

All required pre-study chemistries should be done ≤ 4 weeks before registration.

9.1.2. End of Study Treatment and Follow-up Period

Patients will be followed for 2 years from End of Treatment. Patient will be followed by treating physicians as per standard of care.

9.1.3. Duration of Therapy

Patients will receive protocol therapy unless:

- Patients completed the 24 cycles of the treatments.
- Treatment is interrupted for more than 12 consecutive weeks; patient's protocol treatment will be discontinued.

IND#: Exempt

- Extraordinary medical circumstances have occurred. If at any time the constraints of this
 protocol are detrimental to the patient's health, protocol treatment should be discontinued.
- Patient develops progressive disease; then the patient will discontinue protocol therapy.
- Patient develops unacceptable toxicity; then the patient will discontinue protocol therapy.
- Patients may withdraw consent and withdraw from the study at any time for any reason.

9.1.4. Duration of Follow-up

Study Number: MCC 19178

For this protocol, all patients, including those who discontinue protocol therapy early, will be followed for response until progression and for survival for 2 years from the End of Treatment. Patients that discontinue protocol therapy early without documented disease progression may have their scans performed per standard of care. All patients must also be followed through completion of all protocol therapy. Patients removed from study for unacceptable adverse events will be followed until resolution or stabilization of the adverse event.

10. STATISTICAL METHODS

10.1. STUDY DESIGN AND SAMPLE SIZE JUSTIFICATION

10.1.1. Phase I Study

Primary Objectives:

Phase I: To determine the safety and tolerability of concurrent cetuximab and nivolumab in patients with recurrent and/or metastatic HNSCC.

Design and Sample Size: The dose escalation phase of the study will enroll 3 to 6 patients per dose level using a standard 3+3 design.

The MTD will be determined using the following de-escalation rules:

- Patients will be enrolled sequentially and treated at one of the dose levels identified below after the one dose of lead-in cetuximab. An initial set of 3 patients will be enrolled at Dose Level 1. If no DLT (see below for the criteria) is observed during Cycle 1 (4 weeks), then enrollment in the phase II as Dose Level 1 will be initiated.
- If DLT is observed in 1 patient during Cycle 1 (4 weeks), then an additional 3 patients will be enrolled at Dose Level 1 (total 6 patients). If DLT is observed in ≤ 1 of 6 patients, then enrollment in the phase II as Dose Level 1 will be initiated.
- If DLT is observed in 2 or more of 6 patients at Dose Level 1, then the MTD will have been exceeded, and a set of 6 new patients will be enrolled at Dose Level -1. If DLT is observed in ≤ 1 of 6 patients, then enrollment in the phase II as Dose Level -1 will be initiated.

Study Number: MCC 19178 IND#: Exempt

 If ≥ 2 of 6 patients experience DLT at Dose Level -1, then the MTD will have been exceeded. This combination will be determined to be unsafe to conduct the phase II portion of the trial, and the trial will be discontinued.

	Cetuximab: Lead-In Day -14 of Cycle 1 only	Nivolumab: Lead-In Day -14 of Cycle 1 only	Cetuximab: Starting Cycle 1 Day 1, every 2 weeks	Nivolumab: Starting Cycle 1 Day 1, every 2 weeks
Dose Level 1	500 mg/m ²	None	500 mg/m ²	240 mg
Dose Level -1	500 mg/m ²	None	250 mg/m ²	240 mg

The DLT period will start on Cycle 1 Day 1 of cetuximab and nivolumab and end on Cycle 1 Day 28. The toxicity after the lead-in cetuximab (Day -14 before Cycle 1 only) prior to the dosing of cetuximab and nivolumab will not be included to the assessment of DLT.

The target DLT rate is <25%. The MTD will be defined as the dose of cetuximab and nivolumab in which <1 of 3 patients experience a DLT or <2 of 6 patients experience a DLT with the next higher dose having at least 2 patients experiencing a DLT. The MTD is the highest dose at which at most 1 of 6 patients has a DLT.

No dose escalations or de-escalations are permitted within each patient's treatment regimen, although dose delays will be permitted. A patient who is withdrawn from the study before the completion of the first cycle for a reason other than a DLT will be replaced.

This study will utilize the Cancer Therapy Evaluation Program CTCAE version 4.1 for toxicity and event reporting. Dose-limiting toxicities will be observed until patients have completed Cycle 1 (4 weeks).

A dose-limiting toxicity will be defined as any of the following events:

- 1. Grade 3 or 4 immune-related toxicities, including dermatitis, hepatitis, thyroiditis, colitis, and pneumonitis.
- 2. Grade 4 cetuximab-related rash.
- 3. Grade 3 or 4 neutropenia (i.e., absolute neutrophil count < 1000 cells/mm³) that is associated with a fever ≥ 38.5°C or lasting longer than 5 days.
- 4. Grade 3 thrombocytopenia with bleeding or grade 4 thrombocytopenia.
- Any grade 3 or 4 non-hematologic toxicity per NCI CTCAE v4.1 criteria that are probably or definitely related to study therapy, except for alopecia, nausea, and vomiting.

10.1.2. Phase II Study

Primary Objectives:

Phase II Cohort A: To test if the overall survival rate of concurrent cetuximab and nivolumab in patients who had progressed on at least one prior line of treatment for their recurrent and/or metastatic HNSCC exceeds that of the historical data, which has an estimated one-year survival rate of 36%.

Cohort A: We will assume 36% one-year overall survival based on the historical data from nivolumab monotherapy. With our expected 56% one-year overall survival after the combined treatment with both cetuximab and nivolumab, we will need to enroll 45 patients to reach 90% power to see a statistically significant difference ($P \le 0.05$) in overall survival. 45 evaluable patients will be treated at the MTD. In order to be considered evaluable, patients

must complete the lead-in period and receive the C1D1 doses of cetuximab and nivolumab. Non-evaluable subjects will be replaced.

IND#: Exempt

Phase II Cohort B: To test if the 1-year overall survival rate of concurrent cetuximab and nivolumab in patients who has not had any prior treatments for their recurrent and/or metastatic HNSCC exceeds that of the historical data, which has an estimated one-year survival rate of 46%.

Cohort B: We will assume 46% one-year overall survival based on the historical data from pembrolizumab monotherapy. With our expected 66% one-year overall survival after the combined treatment with both cetuximab and nivolumab, we will need to enroll 43 patients to reach 90% power to see a statistically significant difference ($P \le 0.05$) in overall survival. 43 evaluable patients will be treated at the MTD. In order to be considered evaluable, patients must complete the lead-in period and receive the C1D1 doses of cetuximab and nivolumab. Non-evaluable subjects will be replaced.

The sample size was obtained for the one-sample log-rank test from PASS15, with the assumption that accrual will take one year with one-year follow-up.

Secondary Objectives:

Study Number: MCC 19178

 To estimate response rate of patients treated with concurrent cetuximab and nivolumab who have recurrent and/or metastatic HNSCC.

The response rate will be estimated using binomial theory with Wilson's method for the 95% confidence interval.

 To estimate progression-free survival of patients treated with concurrent cetuximab and nivolumab who have recurrent and/or metastatic HNSCC.

The median and 1-year progression-free survival rates will be estimated from the Kaplan-Meier curve with its 95% confidence interval.

• To evaluate the toxicity of the cetuximab and nivolumab combination in this patient population.

The toxicity data will be provided in a table by major toxicity category and for the highest toxicity grade for the patient.

Exploratory Objectives:

 To identify potential biomarkers related to response to concurrent cetuximab and nivolumab in patients with recurrent and/or metastatic HNSCC.

Exploratory analysis to assess the association of potential biomarkers with disease response will be made using logistic regression.

 To determine a quantitative radiomics based on CT and/or PET images as a prognostic biomarker in recurrent or metastatic HNSCC

Exploratory analysis to assess the association of potential radiomics signatures with disease response will be made using logistic regression.

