More recently, the results of a phase III randomized trial of single agent pembrolizumab versus EXTREME (cisplatin + 5-FU + cetuximab followed by cetuximab maintenance) in the first line recurrent and/or metastatic (RM) HNSCC setting (The Keynote 048 trial) revealed a significantly improved overall survival with single agent pembrolizumab compared to the EXTREME regimen in the biomarker selected PD-L1 CPS score > or = to 20 (HR=0.61, P=0.0007) as well as CPS > or = to 1 (HR=0.78, P=0.0086) populations.⁴³ These findings support pembrolizumab monotherapy as a new first line standard of care for the biomarker selected RM HNSCC. Of significance is the favorable safety profile of single agent pembrolizumab in comparison to EXTREME reported in KN048 supporting single agent PD-1

inhibitors as a new standard. The results of KN048 have opened the door for testing novel combination therapies with PD-1 inhibitors in the first line RM setting in HNSCC.

We hypothesize the combination of cetuximab and nivolumab will improve the one-year overall survival as the first line regimen in unselected R/M HNSCC due to the synergy between the two agents that have proven efficacy in R/M HNSCC. Based on these new findings, we will be expanding our enrollment to include patients who are candidates for first line therapy in the recurrent metastatic setting as Cohort B.

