2.2.2. Primary Objective - Phase II

Phase II Cohort A: To determine the 1-year overall survival rate of concurrent cetuximab and nivolumab in patients who had progressed on at least one prior line of treatment for their recurrent and/or metastatic HNSCC.

Phase II Cohort B: To determine the 1-year overall survival rate of concurrent cetuximab and nivolumab in patients who has not had any prior treatments for their recurrent and/or metastatic HNSCC.

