3.3.2. Inclusion Criteria

Study Number: MCC 19178

Patients must have histologically or cytologically confirmed squamous cell carcinoma
of oral cavity, oropharynx, paranasal sinuses, nasal cavity, hypopharynx, or larynx.
Squamous cell carcinoma of unknown primary in cervical lymph node can be included
only if p16 status is positive.

Cohort A:

- Patients must have recurrent or metastatic HNSCC that is not amenable to local therapy with curative intent (surgery or radiation therapy with or without chemotherapy).
- Patients with persistent disease following radiation therapy administered with a chemotherapy sensitizer may also be included.
- Patients must have progressed on at least one prior line of chemotherapy, targeted therapy, palliative radiation and/or biological therapy regimen for their recurrent and/or metastatic HNSCC. However, if patients are likely to be intolerant to standard first-line systemic chemotherapy, the patients are eligible to enroll to this study as the first-line therapy. Additionally, patients with persistent disease or platinum-refractory recurrent disease (recurs within 6 months of last dose of chemotherapy given as a sensitizer to definitive radiation) may enroll in this study as a first-line therapy.
- Prior treatment with a combination of cetuximab and a PD-1/PD-L1 inhibitor is excluded. Prior treatment with cetuximab or a PD-1/PD-L1 inhibitor is allowed as long as not previously given in combination.

Cohort B:

- Patients must have recurrent or metastatic HNSCC that is not amenable to local therapy with curative intent (surgery or radiation therapy with or without chemotherapy).
- Patients with persistent disease following radiation therapy administered with a chemotherapy sensitizer may also be included.
- Patient must NOT have any systemic therapy for recurrent and/or metastatic disease except if given as a part of a multimodality treatment (i.e. re-irradiation and systemic therapy for curable intent of locally recurrent disease).
- Patients that refuse potentially curative salvage surgery for recurrent disease are ineligible.

- Prior treatment with a combination of cetuximab and a PD-1/PD-L1 inhibitor is NOT included.
- Prior treatment with a PD-1/PD-L1 inhibitor is NOT included.

IND#: Exempt

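### Cohort A's objective covers previously treated patients, but its single test against 36% also counts an uncapped number of first-line patients, with no analysis by line of therapy

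*Combined protocol and SAP*

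**What the plan says.** **Objective.** Section 2.2.2 states the Cohort A aim "in patients who had progressed on at least one prior line of treatment for their recurrent and/or metastatic HNSCC". The Synopsis repeats it, and section 10.1.2 turns it into a test against a historical one-year rate of 36%.

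**Eligibility.** Section 3.3.2 (and the Synopsis) gives the matching main criterion, "Patients must have progressed on at least one prior line of chemotherapy, targeted therapy, palliative radiation and/or biological therapy regimen", and then widens it. For patients likely to be intolerant of standard first-line chemotherapy, "the patients are eligible to enroll to this study as the first-line therapy". A further sentence, "Additionally, patients with persistent disease or platinum-refractory recurrent disease", opens a first-line route for those two groups as well. No cap or quota is given.

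**Analysis.** Sections 3.2.4 and 10.1.2 make a patient evaluable on completing the lead-in and receiving the first combination doses; line of therapy plays no part. Section 10.1.2 sets one null for all 45: "We will assume 36% one-year overall survival based on the historical data from nivolumab monotherapy". Nothing in that section breaks results down by line.

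**Cohort B.** Section 1.1.4 adds "patients who are candidates for first line therapy in the recurrent metastatic setting as Cohort B". Its objective in section 2.2.2 is "in patients who has not had any prior treatments for their recurrent and/or metastatic HNSCC", and its null in section 10.1.2 is 46%.

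**The concern.** Followed to the letter, the plan can answer a question that differs from the one in its objective. A positive Cohort A result would naturally be written up as a gain in previously treated patients, although an unknown part of the sample had no prior line. The protocol itself treats line of therapy as important enough to need a separate cohort and a separate null.

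Two misreadings are possible. The pooled test could succeed with no gain in previously treated patients, or a real gain in them could be diluted. With no reporting by line, a reader could not tell which had happened.

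**Working it through.** **Inputs from section 10.1.2.** Null 36%, alternative 56%, N = 45, power 90%, P ≤ 0.05, one-sample log-rank test, one year of accrual plus one year of follow-up. Sidedness is not stated.

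**Step 1: reproduce the sample size.** Assume exponential survival and uniform accrual. The hazard ratio is ln 0.56 / ln 0.36 = 0.568. Under the alternative, the event probability is v1 = 0.575 and the expected null cumulative hazard is v0 = 0.575/0.568 = 1.013. With σ1 = 0.983 the standard deviation per patient of observed minus expected events,

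n = (z_α·√v0 + z_β·σ1)² / (v0 − v1)² = (1.645 × 1.0066 + 1.282 × 0.983)² / 0.438² ≈ 44.3, rounded up to 45.

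The same formula gives 42.9, rounded up to 43, for Cohort B. Both planned sizes reproduce at one-sided 0.05, so that level is used below. The sample-size arithmetic is sound, but it assumes one homogeneous 36% null.

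**Step 2: let first-line patients in.** Each scenario simulates 100,000 trials of 45 patients and counts success when (E − O)/√E > 1.645, with E computed from the 36% null. The documents give neither the first-line share nor these patients' survival; both are assumed.

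| First-line patients among 45 | No benefit; first-line rate 46% | No benefit; first-line rate 30% | Only first-line patients reach 56%; pretreated stay at 36% |
|---|---|---|---|
| 0 | 4.1% | 4.1% | 4.1% |
| 2 | 4.8% | 3.8% | about 6% |
| 9 | 8.0% | 2.6% | 14% |
| 22 | 17% | 1.2% | 44% |

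A test restricted to pretreated patients stays near 4% in all of these scenarios. At one-sided 0.025 the pattern is the same: 1.8% with no first-line patients, and 3.9% to 9.9% with 9 to 22 of them at 46%.

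**Step 3: the neutral case.** Give everyone the same hazard ratio, 0.568. A first-line untreated rate of 25% becomes 0.25^0.568 = 46%, and one of 46% becomes 0.46^0.568 = 64%. Over that range pooled power is 86% to 95% with 9 first-line patients and 73% to 98% with 22, against about 92% (simulated) with none.

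**Step 4: what the positive results mean.** With 9 first-line patients at 46%, the enrolled mix has a true one-year rate of (36 × 36% + 9 × 46%)/45 = 38%. With 22 it is (23 × 36% + 22 × 46%)/45 = 40.9%. Survival in the mix really does exceed 36%, so rejecting the null is correct for the mix. The error lies in attributing the result to previously treated patients.

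**Step 5: the restricted test.** For 36% versus 56%, simulated power is about 86% with 36 pretreated patients and 69% with 23.

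**The case against.** The first-line routes are not hidden. They stand directly beneath the main Cohort A criterion, and the objective can be read as shorthand for the population defined there. That is fair: it makes this a fault of wording and reporting, curable without touching the design.

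A reader might go further and infer that 36% is the wrong benchmark, or that the test's type I error is inflated. The documents support neither. Section 1.1.4 describes the nivolumab trial's patients only as having recurrent and/or metastatic disease. If that trial included platinum-refractory or persistent disease, 36% may suit those entrants. Nor can Cohort B's 46% be assumed for them, since they are a selected group.

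The share may also be small. With 2 first-line patients at 46%, the chance of a positive result with no benefit is 4.8%, and with 5 about 6%. The large figures need a first-line share near one half (22 of 45 is 49%), which no document supports. If all patients benefit equally, 9 first-line patients change power little.

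What stands is that nothing limits the share and nothing in the planned output would reveal its effect.

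**Conclusion.** The mismatch between objective, eligibility and analysis is plain in the text and should be corrected. Its effect on the result cannot be sized or signed from the documents. Under the assumed 30% to 46% range for first-line survival with no benefit, the chance of wrongly crediting previously treated patients runs from about 1% to 17%, against about 4% with no first-line patients. These figures rest on one-sided 0.05, exponential survival and assumed shares.

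A second, less certain point is cohort overlap. Both cohorts carry the sentence "Patients with persistent disease following radiation therapy administered with a chemotherapy sensitizer may also be included", and Cohort B does not exclude chemotherapy-intolerant patients. Patients whose only prior line was palliative radiation satisfy Cohort A's main criterion, while Cohort B bars only prior systemic therapy for recurrent or metastatic disease. Given the remaining criteria, some patients can therefore qualify for both, and the visible text does not say which cohort takes them. A reader might conclude that no rule exists. That does not follow: the registration form and the eligibility checklist are not in our copy.

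**What to change.** - Keep the 45-patient test as primary. State in the objective and conclusions that it covers the population section 3.3.2 enrols: previously treated patients, plus first-line patients who are likely chemotherapy-intolerant or have persistent or platinum-refractory disease.
- Pre-specify, as a supportive analysis, the same one-sample log-rank test against 36% restricted to patients who progressed on at least one prior line.
- Report one-year overall survival with a 95% confidence interval by line of therapy, identifying patients whose only prior line was palliative radiation.
- Draw no conclusion specific to previously treated patients from the pooled result alone.
- Label these analyses post hoc if outcomes have already been reviewed. Section 3.2.2 says phase II accrual has begun, and section 11.5.3 has the Protocol Chair reviewing efficacy endpoints.
- Check the registration form and eligibility checklist for a cohort-assignment rule. If there is none, reconcile sections 1.1.4, 2.2.2 and 3.3.2.

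**Cost.** Some wording and a few analyses. Line of therapy must already be known to check eligibility, and neither the sample size nor the primary test changes. The drawback, to be stated in the plan, is precision. The restricted test has less power (Step 5), and the subgroup intervals are wide: by Wilson's method, 4 of 9 alive at one year gives about 19% to 73%, and 20 of 36 about 40% to 70%.

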1.1.4. PD-1 inhibitors in HNSCC

Study Number: MCC 19178

[figure not shown]
Recently, immunotherapy has become an attractive option in HNSCC. PD-1 is one of the clinically significant checkpoint molecules that have been shown to suppress T-cell function upon binding to its ligands, PD-L1 and PD-L2, which have been shown to be expressed in tumor cells from both preclinical models and clinical settings of cancer patients undergoing immunotherapy. 37,38 Tumor expression of PD-L1 was tightly correlated with clinical responsiveness to nivolumab in the early clinical trials, supporting the adaptive immune resistance hypothesis.³⁹ Both HPV-positive and HPV-negative HNSCC have been shown to express PD-L1.40,41 Nivolumab is a potent and highly selective humanized monoclonal antibody that binds PD-1 and blocks the interaction between PD-1 and its ligands, PD-L1 and PD-L2. A phase III clinical trial comparing nivolumab versus investigator's choice chemotherapy (methotrexate, docetaxel, or cetuximab) showed an overall survival benefit with nivolumab, with a 7.5-month median overall survival versus 5.1 months with investigator's choice chemotherapy (hazard ratio 0.7, P = 0.01) and minimal toxicities in recurrent and/or metastatic HNSCC patients.⁴² Objective response rate of nivolumab was 13% versus 5.8% with investigator's choice chemotherapy. In a subset analysis, patients with PD-L1 expression had higher response rates than patients without PD-L1 expression, and HPV-positive patients showed longer overall survival than HPV-negative patients. Although these are encouraging results, the clinical benefit was seen in only a limited number of patients. Thus, identification of combination regimens is urgent in the management of HNSCC.

[figure not shown]

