6.1.1. Measureable Lesions

Measureable lesions should be selected on the basis of their size (those with the longest diameters) and their suitability for accurate repeated measurements. The sum of the longest diameters of all measurable lesions and shortest diameters of all measurable malignant lymph nodes will be calculated at baseline and reported as the baseline sum of longest diameters. The sum longest diameter will be used to characterize the objective overall tumor response. For lesions measurable in 2 or 3 dimensions, always report the longest diameter for tumors and the axis perpendicular to the longest axis for lymph nodes at the time of each assessment.

- Complete Response (CR): The disappearance of all measurable lesions.
- Partial Response (PR): At least a 30% decrease in the sum of the longest diameters of measureable lesions, taking as reference the baseline sum longest diameter.

- Progressive Disease (PD): At least a 20% increase in the sum of the longest diameters of target lesions, taking as reference the smallest sum longest diameter recorded since the baseline measurements, or the appearance of one or more new lesion(s).
- Stable Disease (SD): Neither sufficient shrinkage to qualify for partial response nor sufficient increase to qualify for progressive disease. To be assigned a status of stable disease, measurements must have met the stable disease criteria at least once after study entry at a minimum interval of 6 weeks.

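### Biomarker and radiomics analyses rest on logistic regression of few responders, with no cohort term, small-sample method or supporting tumour-change outcome

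*Combined protocol and SAP*

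**What the plan says.** Section 10.1.2 sets one biomarker objective for both cohorts: "To identify potential biomarkers related to response to concurrent cetuximab and nivolumab in patients with recurrent and/or metastatic HNSCC". Its analysis is a single sentence, "Exploratory analysis to assess the association of potential biomarkers with disease response will be made using logistic regression", and radiomics has a parallel one, "Exploratory analysis to assess the association of potential radiomics signatures with disease response will be made using logistic regression". Neither names covariates, a cohort term, stratification, or a penalised or exact method. Neither says whether the cohorts are pooled or analysed separately.

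The cohort sizes come from the survival calculation in the same section: "we will need to enroll 45 patients to reach 90% power" for Cohort A and "we will need to enroll 43 patients to reach 90% power" for Cohort B. No response rate is projected for the combination. Section 1.1.4 reports "Objective response rate of nivolumab was 13% versus 5.8"% for the comparator, section 1.1.3 gives 13% for cetuximab alone, and section 1.1.1 gives 10 to 40% across agents.

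Response is derived from a measured quantity. Section 6.1.1 states: "The sum longest diameter will be used to characterize the objective overall tumor response". It sets partial response at a 30% fall from baseline.

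Under section 3.3.2, Cohort A may have had earlier cetuximab or PD-1/PD-L1 therapy, though not the two combined. Cohort B excludes earlier PD-1/PD-L1 therapy, and allows earlier cetuximab only as a radiation sensitiser.

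**The concern.** Logistic regression named without qualification would normally be read as ordinary maximum likelihood. Three weaknesses follow.

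- With a handful of responders in a cohort, the estimate for a binary marker may not exist or may be wildly imprecise.
- The objective spans two cohorts with different treatment histories. Earlier checkpoint-inhibitor exposure could plausibly affect both immune markers and the chance of response. A pooled fit without a cohort term could then flag markers that only tell Cohort A from Cohort B.
- Reducing measured shrinkage to yes or no discards information that is already collected.

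At stake is the yield of mandatory serial blood samples and optional research biopsies. No treatment decision and no primary conclusion depends on this analysis.

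**Working it through.** **Cohort sizes.** The plan's own figures reproduce. A one-sample log-rank test with exponential survival, one year of uniform accrual, one year of follow-up, one-sided 0.05 and 90% power gives 44.3, rounded to 45 (36% v 56%), and 42.9, rounded to 43 (46% v 66%). Sidedness is not stated; two-sided 0.05 by the same formula gives 55 and 53. The total is 45 + 43 = 88. The biomarker analysis has no responder count or power of its own to reproduce.

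**Responders and information kept.** Expected responders are N × p. The share of information kept by a binary cut of a normal outcome is φ(z)² / [p(1 − p)], where z is the p-quantile of the standard normal. At p = 0.13, z = −1.126 and φ = 0.2115, so 0.2115² / 0.1131 = 0.396. At p = 0.25, φ = 0.3178, so 0.3178² / 0.1875 = 0.539. The 25% rate is an assumption; the 10 to 40% range is shown around it.

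| Response rate | Cohort A | Cohort B | Pooled | Kept | Lost |
|---|---|---|---|---|---|
| 10% | 4.5 | 4.3 | 8.8 | 0.342 | 66% |
| 13% | 5.9 | 5.6 | 11.4 | 0.396 | 60% |
| 25% | 11.3 | 10.8 | 22.0 | 0.539 | 46% |
| 40% | 18.0 | 17.2 | 35.2 | 0.622 | 38% |

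The loss reaches half only when response is about 21% or lower.

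**Empty cells.** An empty cell in the marker-by-response table leaves no finite maximum-likelihood estimate. Let k of n patients carry a marker of prevalence m, with response probability p1 in carriers and p0 in others. The chance of no empty cell is Σ Bin(k; n, m) × [1 − (1 − p1)^k − p1^k] × [1 − (1 − p0)^(n−k) − p0^(n−k)]. For n = 45, 13% response overall, true odds ratio 1 or 3 and m from 20 to 50%, some cell is empty in about 10 to 31% of trials. For the pooled 88 at 13% it is 10% or less.

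**Cohort confounding if pooled.** Assume response of 13% in A and 30% in B, marker prevalence of 30% in A and 60% in B, and no marker effect within either cohort. Expected counts are:

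- marker present, response: 45(0.3)(0.13) + 43(0.6)(0.30) = 9.495
- marker present, no response: 45(0.3)(0.87) + 43(0.6)(0.70) = 29.805
- marker absent, response: 45(0.7)(0.13) + 43(0.4)(0.30) = 9.255
- marker absent, no response: 45(0.7)(0.87) + 43(0.4)(0.70) = 39.445

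The pooled odds ratio is (9.495 × 39.445) / (29.805 × 9.255) = 1.36. With 25% response in B it is (8.205 × 40.305) / (31.095 × 8.395) = 1.27. Simulated type I error is about 0.09 to 0.10 in the first case and 0.07 in the second. A cohort term brings both to about 0.05 to 0.06.

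For a continuous marker shifted by 0.5 SD between cohorts, the unadjusted error is 0.054 with equal response rates, 0.068 at 13%/25% and 0.108 at 13%/36%. With a cohort term it is 0.054 to 0.056.

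**Power.** The simulation used 88 patients, normal tumour change measured in everyone, a linear marker relation, two-sided 0.05 and 4,000 runs.

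| Marker correlation with tumour change | Logistic on response (13% to 25%) | Continuous change plus cohort |
|---|---|---|
| 0.3 | 0.44 to 0.55 | 0.81 to 0.82 |
| 0.4 | 0.67 to 0.81 | 0.97 to 0.98 |

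**The case against.** Several stronger readings are tempting, and the documents do not support them.

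- **That half or more of the information is always lost.** At 25% response the loss is 46%, and at the 40% top of the background range it is 38%.
- **That the plan mixes cohort and marker effects.** It does not say that the cohorts are pooled. Confounding needs pooling, plus both response and marker differing by cohort; the sparsest counts arise when cohorts are analysed separately. The two problems are alternatives.
- **That logistic regression is the only biomarker analysis anywhere.** The contents list a section 8.3 on biomarker evaluations whose body was not in the text available for this review. The statement is limited to section 10.1.2.
- **That percent change should replace response.** The objective names response, and logistic regression answers it directly. Under section 6.1 and Appendix 1, new and non-target lesions also count, so shrinking target lesions with a new lesion is progression.

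The power gain also depends on the model above. If 20% of patients lack a scan and take the worst rank independently of the marker (88 patients, correlation 0.3), logistic gives 35% and rank correlation 41% at 13% response. At 25% response logistic wins, 45% to 38%. If the marker acts only on the chance of response (odds ratio 2 per SD, 13% response), logistic has 55% and rank 21%. These results stand, and they are why tumour change belongs in a supporting role.

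Instability should not be overstated for continuous markers either: with 45 patients, 13% response and correlation 0.4, complete separation occurred in about 0.2% of runs. The risk of infinite estimates is mainly for binary markers within a cohort.

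**Conclusion.** The point holds in limited form, as an inexpensive improvement to an exploratory analysis. Section 10.1.2 leaves cohort handling open and states no method suited to 6 to 11 responders per cohort or 11 to 22 pooled. Those counts rest on the 13% single-agent rate and an assumed 25%; the full 10 to 40% range gives about 4 to 18 per cohort and 9 to 35 pooled.

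The confounding is conditional and moderate. The null odds ratios and error rates come from chosen response rates and marker prevalences, not from trial data. The 46 to 60% information loss assumes normal tumour change, and the power advantage also assumes a linear marker relation and a measured value for every patient. Nothing here affects the primary survival tests.

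**What to change.** Amend the two exploratory analysis sentences in section 10.1.2, for biomarkers and radiomics alike.

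1. Keep response as the main outcome. Fit it by Firth-penalised logistic regression with a cohort term, and state that the cohorts are combined on that basis.
2. Add best percent change in the sum of diameters as a supportive outcome, analysed by rank-based regression stratified by cohort.
3. State in advance how patients without a post-baseline scan are handled, for example worst rank after progression or death before a scan, and report how many there are.
4. Say whose measurements are used. Section 6.2 sends images from non-Moffitt sites for central review only when the patient responded, so one reading source should serve all patients in the supportive analysis.

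No new data, visits or patients are needed if site readings are used. The cost is protocol wording, minor programming and slight shrinkage of the odds-ratio estimates. In the simulations the cohort term cost essentially no power (0.437 without it and 0.436 with it, at correlation 0.3 and 13% response). The supportive outcome ignores new and non-target lesions, and its gain depends on how many patients lack a scan.
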